The DUS will identify a minimum of 600 patients newly initiating RPV-containing regimens and 600 patients newly initiating EFV-containing regimens and captured in one or more of the HIV cohorts currently established in Europe. Exposure to RPV-containing regimens will be measured by the presence of prescription records for the fixed dose combination (FDC) of RPV with emtricitabine/tenofovir (TRUVADA TM (Gilead)) or single agent tablets of RPV among the patient data. Exposure to EFV will be measured by the prescription records for the available formulations of EFV in patient data. Information on drug use, including dispensing date, dose prescribed, quantity dispensed and the length of drug supply, will also be captured from the prescription records in the cohort database. The sample size targets will produce an error rate of no more than 5% for the proportions estimated. A minimum of 600 RPV-treated patients will be included in the DUS to assess the proportion of appropriate use of RPV-containing regimens. The study period will start at the date of market availability of RPV-containing products in the participating counties and will end when in total 600 patients from each treatment group have been included in the study and followed for 12 months, until virologic failure, or lost to follow-up, whichever occurs first.

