Given the recognized limitations of assessing food intake and treatment adherence in large observational studies conducted over several months, the feasibility of collecting food intake and treatment adherence data within the cohorts will be further explored. Currently, the HIV cohorts do not routinely collect data on ARV treatment adherence or pill intake with food. Optimally, HIV cohort data collection protocols will be modified for all RPV-treated patients to facilitate data collection on both ARV treatment adherence and pill intake with food at each patient visit. Under this scenario these measures will be added to the analysis described above. A nested case-control study will be conducted to address the CHMP's concerns on the effects of food intake on virologic failure among patient treated with RPV, while also evaluating ARV treatment adherence. The objective of the nested case-control analysis is to quantify the risk of virologic failure associated with adherence to ARV treatment and dietary instructions. Patients who experience virologic failure while under observation in the DUS will be selected into the study as cases. Patients who do not experience virologic failure while under observation and have similar experience with known confounders for virologic failure will be matched to cases using the incidence-density sampling method. This subgroup of patients from the DUS will be contacted and have their ARV treatment adherence and pill intake with food assessed through a one-time questionnaire assessing both adherence parameters over the past seven days. The methodology for the nested case-control study is provided in parallel with the DUS in this protocol.

ABBREVIATIONS

AACTG	Adult AIDS Clinical Trials Group
ARCA	Antiretroviral Resistance Cohort Analysis database
ARV	antiretroviral
BMI	body mass index
CHIC	Collaborative HIV cohort
CHMP	The Committee for Medicinal Products for Human Use
CI	confidence interval
CoRIS	Cohort of Spanish AIDS Research Network
DUS	Drug Utilization Study
EFV	efavirenz
FDC	Fixed dose combination
FTC	emtricitabine
FHDH	French Hospital Database on HIV
GPP	Good Pharmacoepidemiology Practice
HAART	highly active antiretroviral therapy
HIV-1	human immunodeficiency virus type 1
IRB	Institutional Review Board
J&JPRD	Johnson & Johnson Pharmaceutical Research and Development LLC.
MAR	missing at random
MCAR	missing completely at random
MNAR	missing not at random
M-PEMS	Modified Prescription Event Monitoring Study

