2.1.1. Nested Case-Control Study Design

A nested case-control study will be conducted to evaluate the effects of ARV treatment adherence and pill intake with food on the risk of virologic failure with RPV. Information on food intake associated with taking RPV and ARV treatment adherence during the last 7 days will be collected retrospectively through a self-reported questionnaire in a smaller sample of RPV-treated patients nested within the DUS. Patients will be informed that their responses are confidential and have no consequences for their treatment. Cases for the case-control study will comprise all RPV-treated patients who experience virologic failure. For each case, four control patients without virologic failure will be chosen using incidence density sampling from the defined cohort of RPV-treated patients in the DUS. Incidence density sampling involves matching each case to a sample of those who are at risk at the time of case occurrence. This sampling method has been found to result in an unbiased estimate of the incidence rate ratio. The control patients will be matched on potential confounders for virologic failure, eg. age, sex, weight or body mass index (BMI), ethnicity, CD4 cell count, pre-treatment viral load, route of HIV infection, co-infection with hepatitis B/C, HIV treatment status (naïve/experienced), and depression. Risk of virologic failure associated with adherence to ARV treatment and dietary instructions will be quantified.

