4.1.2. Nested Case-Control Sample Size

The power and detectable odds ratio for the nested case-control study will be based on the number of patients experiencing virologic failure while under observation in the DUS. The power ranges for detectable odds ratios based on the observed number of cases at alpha=0.05 is given Table 1 below. For example, based on an alpha of 0.05, a control to case ratio of 4:1, and an adherence level of 80% or greater in 50% of patients, approximately 40 cases would be needed for a minimally detectable odds ratio of 3.0 with 80% power. For a minimally detectable odds ratio of 2.0, approximately 90 cases would be needed.

Table 1. Sample size and study power for minimally detectable odds ratio assuming a two-sided test, 5 percent alpha level, an adherence level of 80% or greater in 50% of patients, and a 4:1 ratio of controls to cases.

Detectable OP								
$\frac{\text{Detectable OR}}{25} = 25 \qquad 4 \qquad 5$								
Cases	1.5	2	2.5	3	5.5	4	5	
0	0.0249979	0.0249979	0.0249979	0.0249979	0.0249979	0.0249979	0.0249979	
10	0.0788996	0.1456193	0.2129961	0.2757540	0.3321963	0.3821915	0.4649655	
20	0.1199695	0.2577778	0.3968270	0.5174057	0.6151327	0.6920104	0.7982529	
30	0.1603557	0.3671945	0.5590526	0.7033559	0.8024057	0.8678758	0.9386928	
40	0.2006102	0.4692415	0.6894629	0.8283160	0.9066258	0.9489490	0.9838703	
50	0.2406664	0.5610976	0.7878403	0.9052049	0.9585720	0.9817546	0.9961780	
60	0.2803320	0.6415215	0.8586668	0.9496126	0.9825155	0.9938649	0.9991643	
70	0.3193976	0.7103878	0.9078456	0.9740491	0.9929161	0.9980363	0.9998286	

0.3576683 0.7682871 0.9410123 0.9869870 0.9972264 0.9993967 0.9999667 80 0.9999938 90 0.3949750 0.8162206 0.9628471 0.9936230 0.9989453 0.9998210 0.9999989 100 0.9969370 0.9996089 0.9999484 0.4311767 0.8553823 0.9769310

Measurements 4.2.

4.2.1. **Exposure Definition and Measures**

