Exposure to RPV will be determined by the presence of prescription records for the FDC of FTC/RPV/TDF or single agent of RPV among patient data. Relevant drug codes will be used to identify RPV-containing regimens in the HIV cohorts. The baseline date for exposure follow-up (index date) for a patient within a given treatment group will be defined by first prescription of RPV or EFV-containing regimens. Duration of exposure will be based on dispense date and days of supply for each dispensed prescription. Exposure to RPV or EFV-containing regimens will be considered discontinued if the prescription is not refilled within a specified interval of time (e.g. twice the days' supply) of the previous prescription. Switches from one drug to another will be captured and time on drug will be defined by the exposure periods. The total length of exposure to a given drug will be the time between start and stop periods of exposure to the same drug.

4.2.1.1. **Exposure Definition in Nested Case-Control Study**

For the nested case-control analysis, exposure will be based on 1) level of daily medication adherence, and 2) level of adherence to food recommendations. Cases and matched controls that are selected will be asked to retrospectively report via a questionnaire how often they took their HIV medication during a specified time period and how often RPV was taken with food. A single item querying the number of prescribed doses the participant had missed in a specified time period will be used, as follows:

"How many doses of your complete HIV regimen did you miss in the last 7 days?"

"For those days you missed, what component of your HIV regimen did you miss?" (If applicable)

"How often did you take RPV with food in the last 7 days?"

Since RPV dosing is once-daily, number of doses taken is equivalent to number of days the medication is taken. A 7-day recall period is proposed for this analysis as it has the advantage of including a weekend, during which adherence is often problematic. Further, DATE (6 September 2011) 20

longer recall periods (7-day vs. 1-3 day) may yield more useful data for once-daily ART dosing since there are too few dosing times in a very brief recall period to capture variations in adherence behaviors (Simoni, 2006).

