4.4. Missing Data Handling

An evaluation of missing data will be conducted to assess the assumptions under which inference is valid. Missing data will be categorized into: missing completely at random (MCAR) in which there is no difference in subjects with missing data and those with complete data; missing at random (MAR) in which missing data are based on known or observed values of the collected variables, but not unmeasured data; and missing not at random (MNAR) where missing data is dependent on variables not measured. The evaluation will consist of comparing the distribution of the observed variables for patients with complete data with the distribution of observed variables for patients with missing data. Strategies for managing missing data may include limiting the analysis to patients with complete data or missing data imputation to estimate the value of the missing data.

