5. STUDY LIMITATIONS

The proposed study is based on analysis of medical and prescription records from databases maintained by HIV cohorts in Europe. The following limitations should be considered:

There is potential misclassification of the diagnosis or the outcomes of interest.

Attribution of loss of virologic control to failure to follow RPV-containing products' SmPC may not be feasible given the multiple factors and dynamics salient to virologic control

Measurement of adherence to treatment regimens are difficult to assess with reliability beyond prescription refills. Reasons for switch of ARV treatment may be captured inconsistently across the HIV cohorts. Adverse events during the course of RPV or EFV-treatment will be described in aggregate; it is not possible or appropriate to assess the causality of individual cases.

Daily measurement of patient food intake with RPV-containing regimens is highly problematic in any study given the time required to measure diet consistently and accurately over the course of the study period. Associations between patient diet measurement and loss of virologic control are likely highly unreliable given misclassification of diet and consistent measurement of dietary intake. Furthermore, a thorough measurement using complicated instruments of the patient's dietary intake may result in changes in dietary behavior to an extent that the behavior becomes unrepresentative of true intake in the 'real world' setting.

Self-report of treatment adherence is susceptible to recall bias and social desirability bias. Self-reported measures reflect only short-term or average adherence and may often overestimate it, particularly when queried retrospectively.

DUS include bias related to the observational nature of the data and potential lack of data due to loss to follow-up or essential data not collected as routine fields. These studies are also subject to real-world prescribing practices that may not provide sufficient patient numbers to meet study goals of ascertainment within a reasonable timeframe. The feasibility evaluation and design assessment of the study are intended to better understand and adjust for these limitations as well as to estimate the probability to meet study goals of ascertainment within a reasonable timeframe.

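### Nested case-control power is read from the number of virologic failures, but only failures with a completed questionnaire and at least one responding control can be analysed

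*Protocol*

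**What the plan says.** - **Power basis (section 4.1.2).** "The power and detectable odds ratio for the nested case-control study will be based on the number of patients experiencing virologic failure". Table 1 lists power by number of cases, "assuming a two-sided test, 5 percent alpha level, an adherence level of 80% or greater in 50% of patients", with four controls per case. The text gives two examples: about 40 cases for an odds ratio of 3.0 at 80% power, and about 90 cases for 2.0.
- **Who is a case (section 2.1.1).** "Cases for the case-control study will comprise all RPV-treated patients who experience virologic failure".
- **Where exposure comes from (Synopsis and section 4.2.1.1).** "This subgroup of patients from the DUS will be contacted and have their ARV treatment adherence and pill intake with food assessed", and "Cases and matched controls that are selected will be asked to retrospectively report via a questionnaire". The recall window is seven days.
- **Analysis (section 4.5.4).** Conditional logistic regression on individually matched sets.
- **Missing data (section 4.4).** Possible strategies include "limiting the analysis to patients with complete data" or imputation. Neither is chosen. Patients with complete and incomplete data will be compared.
- **Dispensing data (Synopsis).** "Information on drug use, including dispensing date, dose prescribed, quantity dispensed and the length of drug supply, will also be captured" from the prescription records. Section 4.2.1 uses dispensing date and days of supply to define how long a patient is exposed, but section 4.2.1.1 does not use them for the adherence exposure.
- **Alternative route (Synopsis and section 1.1).** Ideally, adherence and food intake would be recorded at each visit for all RPV-treated patients. Feasibility is still to be assessed.

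**The concern.** The count that drives power and the count that can be analysed are different. Every RPV failure is a case, but a failure that cannot be reached or does not answer has no value for either exposure. Unless that value is imputed, its matched set, including any controls who answered, contributes nothing to the conditional likelihood. A responding case with no responding control is lost in the same way. The protocol gives no response rate, no inflation for non-response and no rule for replacing controls who do not answer.

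The nested study is there to address the CHMP's question on food intake, together with adherence. If the team counts 40 or 90 failures, reads about 80% power from Table 1 and then has fewer usable sets, a null result would be given more weight than it deserves. A second issue is who answers. If response depends on failure and adherence jointly, the odds ratio among responders differs from the one among all RPV-treated patients. The limitations section names recall and social desirability bias and a general lack of data, but not questionnaire non-response.

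**Working it through.** **Inputs from section 4.1.2 and Table 1:** two-sided alpha 0.05, exposure prevalence p0 = 0.5 in controls, four controls per case, 40 cases at OR 3.0 (Table 1: 0.828) and 90 cases at OR 2.0 (Table 1: 0.816). **Assumed:** the response rate r, because the documents give none.

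**Formula (unmatched approximation, n cases, m controls per case):**

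- p1 = p0·OR / (1 + p0·(OR − 1)), and p̄ = (p1 + m·p0)/(m + 1)
- Power = Φ{ [ |p1 − p0| − 1.96·√(p̄(1 − p̄)(1 + 1/m)/n) ] / √([p1(1 − p1) + p0(1 − p0)/m]/n) }

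**Step 1: reproduce the plan.**

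- OR 3.0, n = 40: p1 = 0.75 and p̄ = 0.55. Power = Φ[(0.25 − 1.96 × 0.0879)/0.0791] = Φ(0.98) = 0.837.
- OR 2.0, n = 90: p1 = 0.667 and p̄ = 0.533. Power = Φ[(0.1667 − 1.96 × 0.0588)/0.0562] = Φ(0.91) = 0.820.

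Dupont's matched formula with no exposure correlation gives 0.838 and 0.820. Both methods agree closely with Table 1, so the table is sound for analysed cases.

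**Step 2: margin.** The same formula reaches 80% power at 37 cases (OR 3.0) and 86 cases (OR 2.0). The margin is used up when case response falls below 37/40 = 92% or 86/90 = 96%.

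**Step 3: apply response r.** Analysed cases = failures × r. Column A keeps four responding controls per case. Column B lets the ratio fall to 4r because lost controls are not replaced.

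| r | 40 failures, OR 3.0: A | B | 90 failures, OR 2.0: A | B |
|---|---|---|---|---|
| 1.0 | 0.837 | 0.837 | 0.820 | 0.820 |
| 0.9 | 0.794 | 0.784 | 0.777 | 0.768 |
| 0.8 | 0.742 | 0.719 | 0.726 | 0.705 |
| 0.7 | 0.679 | 0.642 | 0.667 | 0.630 |
| 0.6 | 0.606 | 0.552 | 0.597 | 0.545 |

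Table 1 shows the same loss directly: 30 cases at OR 3.0 give 0.703, and 70 cases at OR 2.0 give 0.710.

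**Step 4: failures needed** = cases / r, rounded up.

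| r | for 40 responding cases | for 90 responding cases |
|---|---|---|
| 0.9 | 45 | 100 |
| 0.8 | 50 | 113 |
| 0.7 | 58 | 129 |
| 0.6 | 67 | 150 |

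**Step 5: selection.** Observed OR = true OR × (response of non-adherent ÷ adherent cases) ÷ (response of non-adherent ÷ adherent controls). All response rates here are illustrative.

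- Non-adherent cases 60%, all other groups 80%: factor 0.75, so 3.0 becomes 2.25 and 2.0 becomes 1.5.
- Non-adherent controls 60%, all other groups 80%: factor 1/0.75, so 3.0 becomes 4.0 and 2.0 becomes 2.67.
- Response depends on adherence alone (80% and 60% in both cases and controls): factor 1, no bias.

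**The case against.** The strongest reply is that section 4.1.2 promises nothing. It fixes no number of cases and no power. Table 1 is a look-up, and the 40- and 90-case figures are examples. That stands. A reader might infer that the protocol states a power it will not deliver, but the documents do not support this: the table is correct once it is entered with the cases actually analysed.

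Second, section 4.4 allows imputation as well as restriction to complete data, and plans a comparison of complete and incomplete patients. Imputation models and responder sensitivity analyses can be left to a statistical analysis plan that is not shown. That also stands, and their absence is no part of this point.

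Third, visit-based collection would largely remove the problem. True, but its feasibility was open, and the questionnaire is the method described for the case-control study.

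Fourth, self-report was a considered choice. Section 1.1 says that quantitative measures, including refill monitoring, are limited by cost and labour. A reader might take the limitations section to name refills as the reliable adherence measure. It says less: "Measurement of adherence to treatment regimens are difficult to assess with reliability beyond prescription refills". This supports a supplementary refill analysis, not replacement of the questionnaire.

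Finally, a case needs a viral load measured under observation, so it was in care around the time of failure, and the delay before contact is not fixed. Response could be high. The objection limits the likely size of the loss but does not remove the mismatch in units.

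**Conclusion.** The point holds in a limited form. Power is tied to failures while the analysis can use only responding cases with at least one responding control, and nothing in section 4.1.2 bridges the two. With four responding controls kept, an assumed 80% response takes power from 0.84 to 0.74 (40 failures, OR 3.0) and from 0.82 to 0.73 (90 failures, OR 2.0). At 60% it is 0.61 and 0.60. These figures rest on an assumed response rate, on Table 1's own 50% prevalence, on no imputation of missing exposure, and on visit-based collection not being available.

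A reader might go further and infer that the odds ratios must be pulled towards 1. That does not follow. Bias requires response to depend on failure and adherence jointly, the documents give no evidence on this, and the direction depends on which group under-responds. The loss of precision needs no such assumption.

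**What to change.** 1. **Section 4.1.2.** Index Table 1 and the 40- and 90-case examples to cases with a completed questionnaire and at least one responding matched control. State the failures needed under an assumed response: 45 to 67 for 40 cases and 100 to 150 for 90 cases, at 90 to 60%. *Cost:* wording, and a less favourable figure.
2. **Sections 4.2.1.1 and 4.5.4.** Add a supplementary conditional logistic model of refill adherence, defined as days' supply divided by days elapsed from the first RPV prescription to the case's failure date, with the same follow-up time for its controls. Include all cases and controls with dispensing records, whether or not they answered, and compare responders with non-responders on this measure. The window should be described in these words, because section 4.2.1 uses the term index date for the first prescription. *Cost:* one further model, with no added patients or contacts.

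**Limits of the second change.** Refill adherence covers a longer period than seven-day recall, so it is a different exposure. It depends on the chosen cohorts supplying dispensing data, and cohort selection was still subject to feasibility assessment. It cannot measure intake with food, so the questionnaire stays.

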3.1.2. Exclusion Criteria

No specific exclusion criteria will be applied in this study.

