4.2.5. Length of Follow-up

Each patient will be followed for 12 months from the initiation of RPV or EFVcontaining regimens, or until death, loss to follow-up within the cohort, or virologic failure, whichever occurs first. Time varying variables will be recorded at each patient visit.

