will be assigned a propensity score ranging from 0 to 1 that represents the fitted probability of receiving RPV-containing regimens. The scores from EFV-treated patients will be plotted against those for RPV-treated patients. Overlap in the treatment groups based on sample size estimates of approximately 600 patients per treatment group in the propensity space must exist for a comparison of outcomes of interest between the two groups.

Incidence rates of virologic failure, pre-treatment resistance, and treatment-emergent resistance will be calculated for the RPV and EFV-exposed patients. The three primary event rates of interest (incidence rates of virologic failure, pre-treatment resistance, and treatment-emergent resistance) will be analyzed in 3 separate sets of analyses. Additional descriptive analyses will include incidence rates for each drug calculated by dividing the number of events by the total person-exposure time and expressed as the number of events per person-year, and 95% confidence intervals. Analyses of virologic failure will be stratified by HIV treatment status (naïve/experienced) at treatment initiation.

Relative risks comparing the RPV-containing regimens with EFV-containing regimens and 95% confidence intervals will be calculated and appropriate stratified analyses will be conducted for virologic failure and emergence of treatment resistance. Poisson regression models will be used to adjust for the appropriate factors that influence the risk of virologic failure and treatment-emergent resistance. Adjustments for imbalances between the treatment groups before receiving the first dose of RPV or EFV-containing regimens will be applied using accepted methods based on sample size availability and the observed overlap of key patient characteristics based on propensity score construction.

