7.2. Study Completion/Termination

7.2.1. Study Completion

The study will be completed once a minimum of 600 patients have entered each of the RPV and EFV treatment groups and have been followed individually for 12 months from RPV or EFV-containing regimen initiation, death, virologic failure, or loss to follow-up to the HIV cohort, whichever comes first. Interim analyses will be conducted to check the number of RPV-treated patients captured in the DUS and to review the estimated timeframe that will be needed to obtain the required sample size. Updates on patient accrual and timelines for study completion will be provided as part of Periodic Safety Update Reports (PSURs) and Risk Management Plan (RMP) updates. A descriptive report on patient counts and the safety profile of RPV-containing regimens with respect to appropriate use by prescribers and patients will be prepared in alignment with the PSUR schedule.

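### Virologic failure and resistance are ascertained past discontinuation or switch, but the incidence rates divide by time on drug, and no rule matches the events counted to that time.

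*Protocol*

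**What the plan says.** **Follow-up.** Section 4.2.5 follows each patient for 12 months from initiation, "or until death, loss to follow-up within the cohort, or virologic failure, whichever occurs first". Section 7.2.1 repeats the list: "death, virologic failure, or loss to follow-up to the HIV cohort, whichever comes first". The Synopsis and section 3.1 give a similar one. Discontinuation and switching appear in none of them.

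**Events.** Section 4.2.2 times failure from the start of the regimen and does not require the patient to be still on it. The 12-month proportions in 4.5.3 also run from initiation. Section 4.1.2 bases the number of cases on failures that occur under observation in the DUS, not on failures on drug.

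**Person-time.** Section 4.5.3 describes "incidence rates for each drug calculated by dividing the number of events by the total person-exposure time". Under section 4.2.1, exposure "will be considered discontinued if the prescription is not refilled within a specified interval of time", for example twice the days' supply. The section adds "Switches from one drug to another will be captured and time on drug will be defined by the exposure periods" and "The total length of exposure to a given drug will be the time between start and stop periods of exposure to the same drug".

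**Entry.** Section 3.1.2 states "No specific exclusion criteria will be applied in this study", and section 2.1 makes every RPV initiator eligible.

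**Use.** Treatment-emergent resistance and virologic failure are primary objectives (1.3.1). Section 4.5.3 counts their incidence rates among its primary event rates and plans RPV/EFV relative risks and Poisson regression.

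**The concern.** An incidence rate is interpretable when each counted event arises in person-time that is also counted. Here the events are observed up to one end point and the time is cut at an earlier one. A patient who stops at month 3 and fails at month 8 is still under follow-up at month 8, so the failure is recorded, but only three months enter the denominator. If that failure goes into the numerator, the rate for the initiating drug is too high.

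The excess grows with the share of patients who stop and with their failure hazard afterwards. If either differs between RPV and EFV, the rate ratio moves without any true difference between the drugs.

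A related gap concerns patients who start both drugs. Someone who begins EFV in the study period and then switches to RPV meets both entry rules. One later failure can fall within 12 months of both initiations, and nothing says which group is charged with it.

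**Working it through.** **Plan's own figures.** The protocol states no expected incidence rate, rate ratio or discontinuation share, so there is no figure of its own to reproduce on this point. Its precision table (4.1.1) concerns the proportion of appropriate use. It reproduces (1.96 × √(0.95 × 0.05/600) = 0.017, printed as 0.02) but does not bear on the rates.

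**Inputs.**
- On-drug failure rate λ: 0.10 per person-year (assumed) and 0.35 per person-year. The latter is the EFV rate from the cohort study cited in section 1.1. Its reference title describes mainly treatment-experienced patients, so it only sets the scale.
- Share s stopping by 12 months in the absence of failure: 10% to 40% (assumed).
- Post-stop hazard: k times λ, with k = 0.5, 1 or 2 (assumed).
- Follow-up: one year, ended by failure (4.2.5). Death and loss are ignored.

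**Formulas, per patient.**
- Stopping hazard c = −ln(1 − s); h = λ + c.
- On-drug time P = (1 − e^(−h))/h; on-drug events = λP.
- Post-stop events = ∫₀¹ c·e^(−ht)·[1 − e^(−kλ(1−t))] dt.
- Mismatched rate = (on-drug + post-stop events)/P. When k = 1, all events together equal 1 − e^(−λ).

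**One rate (λ = 0.35, s = 20%, k = 1).** c = 0.2231, h = 0.5731 and P = 0.7612. All events = 1 − e^(−0.35) = 0.2953. The mismatched rate is 0.2953/0.7612 = 0.388, an excess of 11%. Both matched pairings return the true rate: on drug, 0.2664/0.7612 = 0.350; over all follow-up, 0.2953/0.8437 = 0.350.

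**One ratio (λ = 0.10 in both groups, k = 1, 10% of RPV and 30% of EFV patients stop).** P = 0.9040 and 0.8028; all events are 0.0952 in each group. The rates are 0.1053 and 0.1185, and the ratio is 0.89 although the true ratio is 1.

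**Overstatement of the rate** (λ = 0.10 / λ = 0.35):

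| k | 10% stop | 20% stop | 30% stop | 40% stop |
|---|---|---|---|---|
| 0.5 | 2.7 / 2.7% | 5.8 / 5.8% | 9.4 / 9.4% | 13.8 / 13.7% |
| 1 | 5.3 / 5.0% | 11.4 / 10.9% | 18.5 / 17.7% | 27.2 / 25.8% |
| 2 | 10.2 / 9.0% | 22.0 / 19.4% | 35.9 / 31.6% | 52.5 / 46.1% |

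**Apparent RPV/EFV ratio when the true ratio is 1** (RPV share stopping vs EFV share; λ = 0.10 / λ = 0.35):

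| k | equal shares | 10% vs 20% | 10% vs 30% | 20% vs 40% |
|---|---|---|---|---|
| 0.5 | 1.00 | 0.97 / 0.97 | 0.94 / 0.94 | 0.93 / 0.93 |
| 1 | 1.00 | 0.95 / 0.95 | 0.89 / 0.89 | 0.88 / 0.88 |
| 2 | 1.00 | 0.90 / 0.91 | 0.81 / 0.83 | 0.80 / 0.82 |

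If the shares are exchanged between the drugs, the ratio is the reciprocal: at 10% vs 30%, from 1/0.94 = 1.06 to 1/0.81 = 1.23.

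**Six-month rule.** Under 4.2.2, a patient with baseline viral load above 500 copies/ml can be declared a failure only after 6 months. If that patient stops at month 3, the on-drug denominator gains 0.25 person-years in which no failure event is possible. An on-treatment rate therefore has a distortion of its own, in the opposite direction.

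**The case against.** Sections 4.2.5 and 7.2.1 govern how long patients are observed, not which events enter a rate. Long follow-up serves other stated aims, such as describing treatment changes and the 12-month proportions. The phrase on incidence rates for each drug in 4.5.3, and the measurement of resistance over the course of therapy in 4.2.2, can be read as on-drug counting. The study calls itself descriptive (4.3.1), and event windows and lags are often left to a statistical analysis plan.

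Much of this stands. A reader might infer that the protocol puts post-stop events in the numerator. No passage says so expressly; the numerator is left open. A reader might also infer that the two rates will be inflated unequally. That needs stopping or post-stop failure patterns that differ by drug, and none are given. Nor is double counting of a failure in both groups a stated rule: it is possible under the entry criteria, but its frequency cannot be estimated from the protocol.

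The argument that this is ordinary SAP detail does not stand. The protocol itself fixes the end of follow-up, the exposure clock and the rate formula, and these three do not fit together. An analysis plan that followed them literally would inherit the mismatch. If the numerator is instead settled later, it could be chosen after the data are seen, for outcomes that the protocol calls primary and compares between drugs.

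**Conclusion.** The point holds as a mismatch in the stated rules. Outcome ascertainment continues regardless of discontinuation or switch, the rate denominator stops with the drug, and nothing limits the numerator to match. Any post-stop event that is counted inflates that drug's rate. The ratio is biased only if discontinuation or post-stop failure differs between RPV and EFV; with equal patterns it stays at 1.00 when the true ratio is 1.

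With an unchanged hazard after stopping, the illustrative overstatement is about 5-27% at 10-40% stopping. A true ratio of 1 becomes about 0.81-0.94 at 10% versus 30% stopping, across post-stop hazards of 0.5 to 2 times. These figures rest on constant hazards, assumed stopping shares and the counting of all post-stop events. They are not a forecast for this study. The 12-month proportions in 4.5.3 divide by patients and are untouched by the mismatch.

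**What to change.** In 4.2.5 and 4.5.3:

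- Name one matched pairing as main, for example all events over all follow-up time from initiation.
- Report the other as a sensitivity analysis: events during exposure plus a stated lag, over the same time including the lag, censored at stop or switch.
- For the on-treatment version, state how patients with baseline viral load above 500 copies/ml who stop before 6 months are handled, since they add time but cannot have an on-drug failure event.
- For the RPV/EFV comparison, add a rule so that one event in a patient who starts both drugs in the study period is not counted in both groups. Keep all RPV initiators in the appropriate-use denominators, as sections 1.3.1 and 2.1 require.

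The cost is wording, one extra analysis run, and fewer events in the on-treatment version.
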